E-FIRM is a registry to track Topera Inc.'s FIRM products in terms of clinical usage, handling, and the safety and effectiveness of FIRM procedures for the treatment of symptomatic atrial fibrillation. There will be at least 150 patients enrolled in this registry

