### Safety endpoint

Safety shall be evaluated both acute and long term.

| Endpoint          | Description  |
|-------------------|--|
| Acute success     | Freedom from major adverse events related to the procedure within seven days of the procedure.   |
| Long-term success | Freedom from cumulative major adverse events related to the procedure (including any repeat procedures required) within one year of the initial procedure. |

---

**Primary Efficacy endpoint** Efficacy endpoints are defined in the table below.

| Endpoint                       | Definition  |
|--------------------------------|---|
| Acute success of FIRM ablation | The acute success of FIRM guided ablation is defined as elimination of the rotors defined by absence of rotors in the FIRMap.   |
| Long term success              | Two sequential endpoints will be used for long term efficacy after the initial AF ablation procedure (only):
(1) Single Procedure Freedom from AF recurrence* at 3 months, and
(2) Single Procedure Freedom from AF recurrence* from 3-12 months after the initial AF ablation procedure

*Freedom from AF recurrence is defined as: No document episodes of AF >30 sec with conventional noninvasive monitoring or, in the case of an cardiac implanted electronic device (CIED), <1% AF noted overall and no episodes of AF>30 sec. |

The design of the registry is summarized in the table below.

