**Registry design**

| Item   | Description  |
|--------|--|
| Design | This is a prospective registry to assess the safety and effectiveness of FIRM procedures for the treatment of symptomatic any type of atrial fibrillation. |

|                     |  |
|---------------------|--|
| Sample Size         | Each site will enroll all FIRM-guided patients undergoing AF ablation into this registry up to at least overall 150 subjects. FIRM-guided ablation is defined as ablating FIRM identified rotors independent of any additional ablation. |
| Randomization       | The registry is non-randomized but consecutive.  |
| Investigators       | Up to 2 investigators per site   |
| Investigative sites | Up to 10 investigative sites within Germany / Europe   |

|                           |   |
|---------------------------|---|
| Patient population | Subjects eligible for participation in the registry should be in accordance to the AF guidelines:

 
Reported incidence of at least two (2) documented episodes of symptomatic AF (paroxysmal, persistent or long standing persistent) during the three months preceding trial entry (at least one episode should be documented by rhythm strip or ECG).
 
Attempt of at least one Class I or III anti-arrhythmia drug with failure defined as recurrence of symptomatic AF or adverse drug effect resulting in stopping the medication.
 
 |
|---------------------------|---|

|                          |   |
|--------------------------|---|
| Registry schedule | The registry visits schedule will follow the standard routine procedure of each site. Proposed activities during the visits are described in the table below. Since this is a registry, these are data items that will be collected, if available, as consistent and applicable with routine and standard clinical care at each site. |
|--------------------------|---|

| Visit Timing                           | Description   |
|--|---|
| Procedure and immediate post-procedure | Cardiac ablation procedure (see "Ablation Procedure" for details). During the procedure, the patient will be monitored for adverse events. Appropriate clinical measures will be taken to treat the adverse event, should one occur.  |

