| Seven-Ten Days Post Procedure          | The following assessments/procedures will be performed: 
 
Symptom and rhythm assessment per defined follow up monitoring
 
Follow up to assess for adverse events
 
  |
| Three Months Post Procedure            | The following assessments/procedures will be performed: 
 
Diagnostic 12-lead ECG
 
48-hr or 72-hr ambulatory continuous ECG monitor (Holter) or CIED interrogation, if applicable
 
Symptom and rhythm assessment per defined follow up monitoring
 
Concomitant anti-arrhythmic medications
 
Adverse events
 
 |
| Six Months Post Procedure              | The following assessments/procedures will be performed: 
 
Diagnostic 12-lead ECG
 
48-hr or 72-hr ambulatory continuous ECG monitor (Holter) or CIED interrogation, if applicable
 
Symptom and rhythm assessment per defined follow up monitoring
 
Concomitant anti-arrhythmic medications
 
Adverse events
 
 |

|                              |  |
|------------------------------|--|
| Twelve Months Post Procedure | 
The following assessments/procedures will be performed:
 
 
• Diagnostic 12-lead ECG
 
• 48-hr or 72-hr ambulatory continuous ECG monitor (Holter) or CIED interrogation, if applicable
 
• Symptom and rhythm assessment per defined follow up monitoring
 
• Concomitant anti-arrhythmic medications
 
• Adverse events
 
 |
|------------------------------|--|

|   |  |
|---|--|
| Ablation procedure description   | Investigators should follow the standard procedure as defined by training from Topera Inc. and appropriate medical judgment for FIRM guided ablation with or without the conventional ablation procedure (mostly PVI) practiced at the individual site.  |
| Post procedure rhythm monitoring | According to routine and standard procedure of the site preferred would be for all subjects without CIED (having AF diagnostic algorithms) to receive a 48 or 72 hour Holter monitor at 3, 6, and 12 months post-procedure.  |
|   | AF symptoms should be documented as recurrent within the follow-up period, further treatment shall be at the discretion of the physician (e.g., drugs, re-ablation, etc.).   |

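### For patients without a CIED, recurrence requires a documented AF episode over 30 sec, so AF seen only on a follow-up 12-lead ECG can literally leave the patient counted as free from AF

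*Protocol*

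**What the plan says.** The Primary Efficacy endpoint table in the protocol Synopsis sets two sequential long-term endpoints after the initial procedure: freedom from AF recurrence at 3 months, and from 3 to 12 months. For patients followed without an implanted device, freedom means "No document episodes of AF >30 sec with conventional noninvasive monitoring". For patients with a CIED it means "<1% AF noted overall and no episodes of AF>30 sec". No clause says how AF on a 12-lead ECG is classified.

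The Registry schedule lists "Diagnostic 12-lead ECG" at 3, 6 and 12 months, alongside a 48- or 72-hour Holter or CIED interrogation. The Registry data collection detail table adds an ECG at discharge and at 1 month. No recording length is given.

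The Holter is not mandatory. Post procedure rhythm monitoring introduces it with "According to routine and standard procedure of the site preferred would be for all subjects without CIED", and the Registry schedule says of all items that "these are data items that will be collected, if available, as consistent and applicable with routine and standard clinical care at each site".

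On size, the Synopsis says "There will be at least 150 patients enrolled in this registry". The design is non-randomized, with no control arm.

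**The concern.** Without a CIED, a patient fails only if an episode longer than 30 sec is documented; otherwise the patient is free. Of the noninvasive tests scheduled, the Holter is the one clearly able to show such an episode, and it may be absent without any departure from the protocol. The test that may remain, the 12-lead ECG, can show AF from start to finish and still not document more than 30 sec.

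Under the literal wording the error goes one way: a patient in AF at the visit is counted as a success. This is most plausible in persistent and long-standing persistent AF, which the registry admits. No comparator shares the error, so it passes straight into the reported freedom rate. With up to 10 sites, some may apply the text and others clinical judgement, so the endpoint could also mean different things at different sites.

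**Working it through.** The protocol gives no figure for this point and no power calculation, so there is nothing to reproduce. The check is one of wording, followed by arithmetic for scale.

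**Wording, step by step**

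1. Without a CIED, the only failure criterion is a documented AF episode over 30 sec (Primary Efficacy endpoint).
2. A visit with an ECG and no Holter is permitted (Registry schedule; Post procedure rhythm monitoring).
3. Assumption: a standard 12-lead tracing lasts about 10 sec. The argument needs only a length of 30 sec or less. Tracings of 10, 12, 20 or 30 sec cannot by themselves document more than 30 sec; one of 31 or 60 sec could.
4. From 1 to 3, AF throughout such a tracing, with no other recording, leaves no documented episode over 30 sec, and the patient literally meets the definition of freedom.
5. Patients with CIED data are not affected.

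**Effect per patient**

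With N = 150, the overstatement from k such patients is k/150:

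- k = 1: 1/150 = 0.67 points
- k = 5: 5/150 = 3.33 points
- k = 10: 10/150 = 6.67 points

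The documents do not give k.

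**Illustrative range for the 3-12 month endpoint**

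Assumed inputs, none from the documents: 20-40% of patients lack Holter and CIED data at a given visit, and 10-20% of those are in AF on the ECG. The visits taken to fall in the window are 6 and 12 months, and a Holter at either is taken to reveal the AF.

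- *Gaps independent between the two visits.* The share missing both is 0.20 × 0.20 = 0.04 to 0.40 × 0.40 = 0.16. Patients affected: 150 × 0.04 × 0.10 = 0.6 to 150 × 0.16 × 0.20 = 4.8. Divided by 150, this is 0.4 to 3.2 points.
- *The same patients miss every Holter*, for example because a whole site does not use it. Patients affected: 150 × 0.20 × 0.10 = 3 to 150 × 0.40 × 0.20 = 12. Divided by 150, this is 2 to 8 points.

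**Comparison with sampling error**

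The 95% half-width is 1.96 × √(p(1 − p)/150). At p = 0.824 it is 6.1 points, and at p = 0.44 it is 7.9 points. These two rates are the 24-month figures that the Introduction quotes from the earlier controlled registry, used here only for scale. The independent case (at most 3.2 points) stays inside the half-width. About ten affected patients (6.67 points) would exceed it at 82.4%.

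**The case against.** The strongest reply is that the 30 sec threshold qualifies the episode, not the recording. A 12-lead ECG is itself conventional noninvasive monitoring, and AF across a whole tracing, read with the symptom and rhythm assessment at the same visit, can reasonably be taken to document a longer episode. Post procedure rhythm monitoring also asks for recurrent AF symptoms to be documented, with no 30 sec test. This stands in part. The protocol nowhere states that such a patient counts as free, so a reader who infers that clear failures are being classed as successes goes further than the text. But the definition does not tell sites to infer a longer episode, and the symptom sentence is not tied to the endpoint. The reply therefore shows that classification could vary by site; it does not remove the gap.

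A reader might also see a contradiction with the entry criterion, which asks that "at least one episode should be documented by rhythm strip or ECG" and sets no duration. That does not hold: eligibility confirms a diagnosis and the outcome sets a threshold, and the two need not share a rule.

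It is also fair to say that much of the harm depends on missing Holter data, whose handling is commonly left to an analysis plan, and that plan is not at hand. What belongs to this point is narrower: the protocol's own endpoint definition has no ECG clause.

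Finally, 2 to 8 points might be taken as the expected bias in the 3-12 month rate. It is not. It applies a per-visit rate to an endpoint that spans more than one visit, and is reached only if the same patients lack every Holter.

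**Conclusion.** The point holds as a defect in the wording of a primary efficacy endpoint. For a patient without a CIED whose only follow-up recording is a 12-lead ECG of 30 sec or less showing AF throughout, the literal definition gives freedom from recurrence, while a site using judgement may record a failure. The literal reading can only raise the single-arm freedom rate.

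The wording defect rests on one outside assumption, the tracing length. The size rests entirely on assumed missingness and AF rates and should be read as a scale, not an estimate. The documents supply only the 150 patients, and that number is a minimum.

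**What to change.** In the Primary Efficacy endpoint definition, state that for patients without a CIED recurrence is either AF present throughout a diagnostic 12-lead ECG, or AF lasting more than 30 sec on a Holter, rhythm strip or other continuous recording. Leave the CIED wording as it is.

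Apply the rule to scheduled and unscheduled ECGs, but only within each endpoint's own window (at 3 months; 3-12 months). Without that limit, AF on a discharge or 1-month ECG would by itself become a failure, which the endpoints do not call for.

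The cost is a short change to the definition. The ECG is already an item in the Registry data collection detail table, so no test is added. The downside is that the reported freedom rate may be slightly lower.

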**Registry design**

| Item   | Description  |
|--------|--|
| Design | This is a prospective registry to assess the safety and effectiveness of FIRM procedures for the treatment of symptomatic any type of atrial fibrillation. |

|                     |  |
|---------------------|--|
| Sample Size         | Each site will enroll all FIRM-guided patients undergoing AF ablation into this registry up to at least overall 150 subjects. FIRM-guided ablation is defined as ablating FIRM identified rotors independent of any additional ablation. |
| Randomization       | The registry is non-randomized but consecutive.  |
| Investigators       | Up to 2 investigators per site   |
| Investigative sites | Up to 10 investigative sites within Germany / Europe   |

|                           |   |
|---------------------------|---|
| Patient population | Subjects eligible for participation in the registry should be in accordance to the AF guidelines:

 
Reported incidence of at least two (2) documented episodes of symptomatic AF (paroxysmal, persistent or long standing persistent) during the three months preceding trial entry (at least one episode should be documented by rhythm strip or ECG).
 
Attempt of at least one Class I or III anti-arrhythmia drug with failure defined as recurrence of symptomatic AF or adverse drug effect resulting in stopping the medication.
 
 |
|---------------------------|---|

|                          |   |
|--------------------------|---|
| Registry schedule | The registry visits schedule will follow the standard routine procedure of each site. Proposed activities during the visits are described in the table below. Since this is a registry, these are data items that will be collected, if available, as consistent and applicable with routine and standard clinical care at each site. |
|--------------------------|---|

| Visit Timing                           | Description   |
|--|---|
| Procedure and immediate post-procedure | Cardiac ablation procedure (see "Ablation Procedure" for details). During the procedure, the patient will be monitored for adverse events. Appropriate clinical measures will be taken to treat the adverse event, should one occur.  |
| Seven-Ten Days Post Procedure          | The following assessments/procedures will be performed: 
 
Symptom and rhythm assessment per defined follow up monitoring
 
Follow up to assess for adverse events
 
  |
| Three Months Post Procedure            | The following assessments/procedures will be performed: 
 
Diagnostic 12-lead ECG
 
48-hr or 72-hr ambulatory continuous ECG monitor (Holter) or CIED interrogation, if applicable
 
Symptom and rhythm assessment per defined follow up monitoring
 
Concomitant anti-arrhythmic medications
 
Adverse events
 
 |
| Six Months Post Procedure              | The following assessments/procedures will be performed: 
 
Diagnostic 12-lead ECG
 
48-hr or 72-hr ambulatory continuous ECG monitor (Holter) or CIED interrogation, if applicable
 
Symptom and rhythm assessment per defined follow up monitoring
 
Concomitant anti-arrhythmic medications
 
Adverse events
 
 |

|                              |  |
|------------------------------|--|
| Twelve Months Post Procedure | 
The following assessments/procedures will be performed:
 
 
• Diagnostic 12-lead ECG
 
• 48-hr or 72-hr ambulatory continuous ECG monitor (Holter) or CIED interrogation, if applicable
 
• Symptom and rhythm assessment per defined follow up monitoring
 
• Concomitant anti-arrhythmic medications
 
• Adverse events
 
 |
|------------------------------|--|

|   |  |
|---|--|
| Ablation procedure description   | Investigators should follow the standard procedure as defined by training from Topera Inc. and appropriate medical judgment for FIRM guided ablation with or without the conventional ablation procedure (mostly PVI) practiced at the individual site.  |
| Post procedure rhythm monitoring | According to routine and standard procedure of the site preferred would be for all subjects without CIED (having AF diagnostic algorithms) to receive a 48 or 72 hour Holter monitor at 3, 6, and 12 months post-procedure.  |
|   | AF symptoms should be documented as recurrent within the follow-up period, further treatment shall be at the discretion of the physician (e.g., drugs, re-ablation, etc.).   |
| Description                      | This is a consecutive registry to assess the safety and effectiveness of FIRM procedures for the treatment of symptomatic atrial fibrillation.   |
| Patient numbering                | Subjects will be assigned consecutive numbers per participating site in combination to a site code   |
| Expertise                        | 
In order to participate in this E-FIRM registry, investigators must have completed the following:
 
 
• Undergone the training provided by Topera, Inc. in the use of the FIRMap Catheter, RhythmView system and analysis of FIRMaps produced by the system
 
 |

## Synopsis

---

**Registry data  
collection  
detail**

Legend:

❖ = Data field

☒ = if applicable

| Event   | Pre-proc | Intra-proc | Discharge | Day 7-10 | 1 month | 3 month | 6 month | 12 month |
|---|----------|------------|-----------|----------|---------|---------|---------|----------|
| Demographics, Medical Hx, Cardiac Dx                              | ❖        |            |           |          |         |         |         |          |
| Lab work (Chemistry, UA, Cardiac enzymes, HCG, LFTs)              | ❖        |            |           |          |         |         |         |          |
| INR (as appropriate on post-ablation f/u)                         | ❖        |            |           | ❖        | ❖       | ❖       | ❖       | ❖        |
| TEE   | ❖        |            |           |          | ☒       | ☒       | ☒       | ☒        |
| Diagnostic 12-lead ECG  | ❖        |            | ❖         |          | ❖       | ❖       | ❖       | ❖        |
| Documentation of Symptomatic AF                                   | ❖        |            |           |          |         |         |         |          |
| Cardiac meds and any AF interventional procedures performed       | ❖        |            |           |          | ❖       | ❖       | ❖       | ❖        |
| NYHA Class Assessment   | ❖        |            |           |          |         |         |         |          |
| AF Symptom and rhythm assessment per defined follow up monitoring | ❖        |            |           | ❖        | ❖       | ❖       | ❖       | ❖        |
| AE review   |          | ❖          |           | ❖        | ❖       | ❖       | ❖       | ❖        |
| Interrogation of CIED for AF burden                               | ☒        |            |           |          | ☒       | ☒       | ☒       | ☒        |
| 48-hr or 72-hr ambulatory continuous ECG monitor                  |          |            |           |          | ☒       | ❖       | ❖       | ❖        |

## Adverse Events

**Overview** All adverse events (unanticipated and anticipated) must be classified as serious or minor.

**Definitions** The table below describes the classifications of adverse events (AE). All major adverse events occurring during the registry will be included in the safety analysis.

| Term        | Definition   |
|-------------|--|
| Serious     | 
Any adverse event which occurs following use of the device and:
 
 
• is life-threatening*;
 
• results in permanent impairment of a body function or permanent damage to a body structure; or
 
• necessitates significant intervention, such as major surgery, to prevent permanent impairment of a body function or permanent damage to a body structure; or
 
• requires hospitalization or an extended hospital stay; or
 
• results in moderate transient impairment of a body function or transient damage to a body structure; or
 
• requires intervention such as medication or cardioversion* to prevent permanent impairment of a body function or damage to a body structure**.
 
 |
| Minor       | 
Any adverse event that occurs following use of the procedure that results in minimal transient impairment of a body function or damage to a body structure, or which does not require any intervention other than monitoring.
   |
| Anticipated | 
Anticipated or known possible adverse events associated with cardiac electrophysiology procedures (see detail listing below in “Anticipated AE”)
  |

| Term          | Definition                                       |
|---------------|--|
| Unanticipated | EU guideline and requirements will be applicable |

\* In this context, the term refers to an event in which the subject was at immediate risk of death at the time of the event; it does NOT refer to an event that might have caused death if it were more severe.

\*\* For example, if the occurrence of a “catheter insertion site hematoma” or an “AV fistula” requires a blood transfusion and/or surgical repair, it should be considered a major adverse event.

**Anticipated AE** Anticipated adverse events include:

| Description   | Description   |
|---|---|
| Discomfort due to insertion/removal of vascular sheaths beyond what is normally observed  | Ventricular arrhythmia requiring defibrillation                                 |
| Hemorrhage and/or hematoma at sheath insertion requiring evacuation or transfusion  | Cardiac tamponade due to perforation  |
| Extremity weakness, swelling, and/or pain   |   |
| Discomfort and/or damage to the skin, muscles, or nerves due to remaining in a supine position for an extended period of time.                  | Nerve injury (diaphragmatic paralysis, pyloric spasm, gastric hypomotility)     |
| Complete AV block   | Air embolism  |
| Nausea /vomiting  | Allergic reaction   |
| Headache different from baseline  | Endocarditis  |
| Hypertension >180 mm Hg systolic (repeated measures)  | Esophageal-atria fistula  |
| Hypotension <80 mm Hg systolic (repeated measures)  | Hemothorax  |
| Brief “black out” periods   | Pericarditis  |
| Shortness of breath/Dyspnea   | Pseudo aneurysm   |
| Feeling of chest pain, skipped beats, and/or rapid heart rate different from baseline   | Pulmonary vein stenosis   |
| Damage to skin from prolonged exposure to x-rays  | Radiation injury  |
| New arrhythmias (not previously documented)   | Renal failure form IV contrast  |
| Arterial injury requiring intervention  | Respiratory failure   |
| Thromboembolism   | Stroke/TIA  |
| Local/systemic infection  | Valvular damage   |
| Pneumothorax  | Pleural effusion  |
| AV fistula  | Pulmonary edema   |
| Thrombophlebitis  | Anemia requiring transfusion  |
| Pulmonary embolism  | Vasovagal reaction  |
| Myocardial infarction   | New pericardial effusion >1 cm  |
| Discomfort and/or damage to the skin, muscles, or nerves due to percutaneous access in excess of usual  | Death (must be reported within the regulation of serious adverse events) |
| Left heart access via trans-septal puncture has known potential adverse events of: cardiac perforation, cardiac tamponade, and embolic events.* |   |

\* Literature reviews have demonstrated that the risk of such events are <1%.  
 Mullins, Charles E. "Trans-septal left heart catheterization: Experience with a new technique in 520 pediatric and adult subjects." Pediatric Cardiology, v. 4, pgs. 239-246 (1983)

**Occurrence** The table below describes actions taken for adverse events that occur during and after the procedure.

| Timing          | Action  |
|-----------------|---|
| Intra-procedure | If the investigator determines that an adverse event occurs while the patient is in the electrophysiology lab (before or during the procedure), the investigator shall manage the patient as he/she would if a similar event occurred during a standard EP procedure. |
| Post-procedure  | Once the patient has left the electrophysiology lab, all medical/surgical management will be carried out in the standard manner for that institution  |

**Reporting SAEs, & deaths** Reporting requirements for deaths or other adverse events considered to be serious or unanticipated are described in the table below.

| Report to                    | Reporting Requirements  |
|------------------------------|---|
| Principal Investigative Site | Must be reported according to the rules of the respective Ethics Committee  |
| EC                           | 
Report of the adverse event to the site's Institutional Review Board is the responsibility of the Principal Investigator.
 
The investigator is responsible for reporting such events to their EC within 10 working days of knowledge of the event.
 
Adverse events clearly unrelated to the device (e.g., broken limb, malignancy) may be reported in accordance with institutional requirements and recorded on CRFs as appropriate
 |

Details are found in Medical Event Report Form "MERF" below.

**MERF** The table below describes the information required on the initial and final MERF reports.

| Information   | Initial | Final |
|---|---------|-------|
| Patient registry number   | ✓       | ✓     |
| Gender  | ✓       | ✓     |
| Date of birth   | ✓       | ✓     |
| Date of procedure   | ✓       | ✓     |
| Adverse experience/complication and classification (major/minor)                  | ✓       | ✓     |
| Period of hospitalization (if required)   | ✓       | ✓     |
| Investigator's opinion as to the relationship of event/complication to the device | ✓       | ✓     |
| The disposition of the device (if returned, provide date)                         | ✓       | ✓     |
| Description of the event or problem   | ✓       | ✓     |
| Classification of event (anticipated/unanticipated and minor/major)               |         | ✓     |
| Date of onset   |         | ✓     |
| Date of resolution  |         | ✓     |
| Date of discovery   |         | ✓     |
| Reporter name, title, and contact information                                     |         | ✓     |
| Patient outcome   |         | ✓     |
| Treatment or therapy used to treat  |         | ✓     |
| Relevant laboratory tests   |         | ✓     |
| Relevant history, including pre-existing medical conditions                       |         | ✓     |
| Suspect device name, part number, and lot number                                  |         | ✓     |

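### CRF recording and the event form turn on relation to the device, while the safety endpoints turn on relation to the procedure, so some procedure-related major events lack a firm recording duty or cannot be classified

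*Protocol*

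**What the plan says.** Four statements in the Protocol bear on this point.

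- **Recording rule** (Adverse Events, Reporting SAEs & deaths, EC row): events clearly unrelated to the device, with a broken limb and malignancy as examples, "may be reported in accordance with institutional requirements and recorded on CRFs as appropriate".
- **Analysis rule** (Adverse Events, Definitions): "All major adverse events occurring during the registry will be included in the safety analysis". No relatedness limit is attached.
- **Endpoints** (Synopsis, Safety endpoint): acute success is "Freedom from major adverse events related to the procedure within seven days of the procedure". Long-term success is "Freedom from cumulative major adverse events related to the procedure (including any repeat procedures required) within one year of the initial procedure".
- **Event form** (Adverse Events, MERF): the only causality item listed is "Investigator's opinion as to the relationship of event/complication to the device".

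The Protocol does not define which device is meant. The products named under Expertise are the FIRMap catheter and the RhythmView system, which serve mapping and analysis. Under Ablation procedure description, FIRM-guided ablation may be done with or without the site's conventional ablation, mostly PVI. Re-ablation is left to the physician.

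**The concern.** Three rules that should use one criterion use different ones. The recording exemption and the causality item look to the device, the endpoints look to the procedure, and the safety analysis takes all major events. The procedure is wider than the device: it can include PVI, sheath insertion, transseptal puncture and later repeat procedures. A major event can thus belong to the procedure and still be judged unrelated to the mapping system.

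Both safety results are rates of freedom from events. A patient whose only endpoint event is not recorded, or cannot be recognised as procedure-related, is counted as a success. An omission of this kind can only make the result look better. An analysis plan cannot settle it from the database alone, because the event or its classification is not there.

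**Working it through.** The Protocol states no expected safety rate, so there is no figure to reproduce. The check compares the rules and then bounds the effect.

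**Step 1. The rules side by side**

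| Rule | Place in Protocol | Criterion |
|---|---|---|
| CRF recording may be discretionary | Adverse Events, EC row | clearly unrelated to the device |
| Causality item on the event form | MERF | device |
| Safety analysis | Adverse Events, Definitions | all major events |
| Acute and long-term endpoints | Synopsis, Safety endpoint | procedure; repeat procedures included in the long-term endpoint |

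**Step 2. What each kind of major event meets**

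1. *Related to the device.* Firm recording duty, and the form captures the relation. No gap.
2. *Unrelated to device and procedure* (the Protocol's own examples, a broken limb or a malignancy). Recording is discretionary. It is not an endpoint event, but the analysis rule still includes it if it is major. The two sentences conflict.
3. *Related to the procedure, judged clearly unrelated to the device.* Recording is discretionary under the EC row. If it is recorded, the listed MERF items give no relation to the procedure. It is an endpoint event all the same.

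The third class is not empty on the Protocol's own terms. A footnote to the definitions treats an insertion-site haematoma or AV fistula that needs transfusion or surgical repair as a major event. The Anticipated AE list includes complications of transseptal puncture and pulmonary vein stenosis. Any of these could be put down to the sheath, the puncture or the PVI rather than to the mapping system.

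**Step 3. Bound per patient**

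Input: minimum enrolment n = 150 (Synopsis; Sample Size). If one patient's only endpoint event is missed, the event-free rate rises by 1/n = 1/150 = 0.67 percentage points. A larger n gives a smaller step. A patient with a second, recorded endpoint event adds nothing.

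**Step 4. Illustration over assumed counts**

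The event counts are assumptions; the Protocol gives none. Event-free rate = 1 − (true − missed)/150, with exact Clopper-Pearson 95% intervals.

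| Patients with an event (assumed) | Missed (assumed) | Event-free rate | 95% CI |
|---|---|---|---|
| 3 | 0 | 98.0% | 94.3 to 99.6 |
| 3 | 3 | 100% | 97.6 to 100 |
| 6 | 0 | 96.0% | 91.5 to 98.5 |
| 6 | 1 | 96.7% | 92.4 to 98.9 |
| 6 | 2 | 97.3% | 93.3 to 99.3 |
| 6 | 3 | 98.0% | 94.3 to 99.6 |
| 12 | 0 | 92.0% | 86.4 to 95.8 |
| 12 | 3 | 94.0% | 88.9 to 97.2 |

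One to three missed patients move the estimate by 0.67 to 2.0 points. In every row that shift lies within the width of the interval, but it always goes in the favourable direction.

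**The case against.** The case for leaving the text alone has real weight.

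- **Placement.** The sentence sits in a row on reporting to the Ethics Committee, directly after the 10-working-day duty. Its evident purpose is to relax EC reporting, and it requires the event to be clearly unrelated. This stands as to intent. But the sentence also speaks of CRFs, so it reaches the data, and its examples are not a limit.
- **Other collection duties.** Adverse event review is a data field during the procedure, at day 7 to 10 and at 1, 3, 6 and 12 months. Every adverse event must be classified, whatever its cause. This limits the exposure. It does not close it, because the Registry schedule collects items only where routine care makes them available.
- **Listed complications.** Pulmonary vein stenosis, nerve injury and oesophageal fistula are on the Anticipated AE list as known risks of electrophysiology procedures. An investigator is unlikely to treat them like a broken limb. This stands, and makes outright omission less likely. It does not supply the missing procedure item on the form.
- **Recovery.** Sites keep source documentation, and other records are available on request. An omitted event could be found by source review, so the loss need not be permanent.

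A reader might infer that endpoint events generally drop out of the database at the investigator's discretion. The documents do not support that. The endpoints count only procedure-related events, and the Protocol's own examples of exempt events would not normally qualify. Only the procedure-related, device-unrelated class is exposed.

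**Conclusion.** The point holds as an inconsistency in the Protocol. Discretionary recording conflicts with the promise to analyse all major events. The recording exemption and the MERF also use a different relatedness criterion from both safety endpoints. Following the text as written can leave a procedure-related major event without a firm recording duty, or recorded without the item needed to classify it.

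The size is unknown. The bound is 0.67 points per patient whose only endpoint event is missed, at n = 150 with all enrolled patients in the denominator; a smaller evaluable set would make each step larger. Nothing in the document says how many events would be missed, so a reader should not take any row of the illustration, such as two missed out of six, as an expected under-count.

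The conclusion rests on two readings: that the device means the sponsor's FIRM products, and that serious in the definitions and major in the endpoints mean the same class. If the device were meant to cover the ablation catheter and sheaths as well, the exposed class would shrink, but the conflict with the analysis rule would remain.

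**What to change.** Separate recording from EC reporting, and align the criterion with the endpoints:

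1. State that every serious (major) adverse event is recorded on the CRF, whatever its relation to the device.
2. Confine the relaxed institutional rule to EC reporting, and to events clearly unrelated to both the device and the procedure.
3. Add a relationship-to-procedure item to the MERF, distinguishing the index from a repeat procedure, beside the existing device item.

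Compulsory entry of every minor unrelated event is not needed for the safety endpoints and would sit badly with a routine-care registry. Recording alone, without the third item, would still leave endpoint status undetermined. The cost is one reworded sentence, one form field and a small number of extra CRF entries. Clinical management is unaffected.
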